10.6.9 Tumor Assessments

Radiographic tumor assessments should be completed as scheduled relative to the date of CID1 regardless of study treatment holds or delay (see [Attachment 1](#)).

Radiographic tumor assessments will include diagnostic quality imaging (CT scan or MRI) of chest/abdomen/pelvis. For patients who have an MRI of the abdomen and pelvis, a CT scan of the chest is also required. An MRI or CT of the brain will also be performed at screening for patients with known or suspected brain metastases and continued post-baseline as clinically indicated. If a CT of the brain is performed, ambiguous results must be confirmed by MRI. For patients with symptoms of spinal compression, MRI of the spine and base of the skull should also be performed. Whole body bone scans will also be performed at screening for patients with known or suspected bone metastases and continued post-baseline as clinically indicated.

The study-specific Imaging Manual should be followed. To ensure image consistency, the same imaging modality and acquisition protocols at the same institution/facility used at screening should be used for subsequent tumor assessments. Ideally contrast-enhanced imaging should be performed at screening and subsequent assessments, including at least post-contrast CT scan of the chest and post-contrast CT or MRI of the abdomen and pelvis. If CT contrast is contraindicated, a non-contrast CT scan of the chest together with contrast-enhanced MRI of the abdomen and pelvis is strongly recommended. If CT or MRI contrast is contraindicated in follow-up tumor assessments after contrast-enhanced imaging at baseline, the same modality without contrast should be performed. All imaging must be acquired and transmitted for central review in original Digital Imaging and Communications in Medicine (DICOM) format per guidelines in the study-specific imaging manual.

For the purpose of patient management and treatment decisions during the course of the study, radiographic response and disease progression will be assessed locally by investigators using RECIST v1.1 ([Attachment 5](#)). For the purpose of robust documentation of radiographic progression per IRC:

- If any doubt or ambiguities exist about radiographic progression, Investigators are encouraged to continue study therapy if the patient is tolerating treatment, repeat

radiographic studies at the next scheduled time, and delay determination of progression until the findings indicating radiographic progression are unequivocal.

- Patients who discontinue study treatment for reasons other than progressive disease by RECIST v1.1 or death will continue to be followed by radiographic tumor imaging until documentation of radiographic progressive disease per RECIST v.1.1, death, initiation of a new anticancer therapy, or withdrawal of consent.
- If study treatment continues beyond Investigator-assessed progression because the patient is receiving clinical benefit from continued treatment (see [Section 11.3](#)), radiographic tumor assessments will also continue until the patient discontinues study treatment. This practice has the benefit of providing radiographic studies for IRC review beyond Investigator-assessed progression, which may be helpful in the case of discordance between the Investigator and the IRC regarding the date of progression.

10.6.10 Tumor Biopsies

10.6.10.1 Archival Tumor Biopsies

Archival tumor samples will be provided from all patients unless the archival sample is unavailable. Archival samples should be collected and shipped according to instructions provided in the laboratory manual. Archival tissue blocks or slides freshly cut from those blocks are strongly preferred, due to the concern of tissue stability after exposure. Archival tissue collected from recent time points before enrollment is preferred because it more accurately reflects the current state of the tumor/microenvironment at the time of study entry.

10.6.10.2 Optional Fresh Tumor Biopsies

At North American sites only, optional tumor biopsies, collected as clinically indicated at any point on the study, may be shared with the Sponsor upon patient consent for exploratory biomarker assessment (e.g., predictive/prognostic biomarkers for response). Unless clinically indicated, biopsies should not be obtained from target lesions being followed for disease assessment prior to documentation of disease progression per RECIST v.1.1.

When obtained, tissue from optional tumor biopsies will be used for 1) the analysis of gene expression levels, 2) immunohistochemical/immunofluorescence analysis, and 3) mutation profiling. Tissue may also be used for the evaluation of additional exploratory biomarkers that are not pre-specified in this protocol based upon new scientific literature and/or preclinical data.

10.6.11 Pharmacokinetic Samples

Pharmacokinetic samples will be collected from all patients. Plasma PK samples will be used to measure concentrations of CB-839, 110826 (the major metabolite of CB-839), and cabozantinib, and may be used to measure other associated analytes by using a validated liquid chromatography tandem mass spectrometry (LC-MS/MS) method of appropriate specificity and sensitivity according to GLP. Blood samples for PK analysis will be collected at the following time points:

- Cycle 2 Day 1: Pre-dose and 2 hr post dose (\pm 30 min). Patients must take their morning dose of CB-839 in the clinic.
- Cycle 3, Day 1: 4 hr and 6 hr post dose (\pm 1 hr). Patients can take their morning dose of CB-839 in the clinic or at home.

The actual time of collection must be noted in the source documents and eCRFs. On Cycle 2 Day 1, patients will have to arrive at the clinic to get their pre-dose PK sample drawn prior to taking their dose in the clinic. Patients must record the times they take their evening dose before Cycle 2 Day 1 and their morning dose on Cycle 3 Day 1 (if they take it at home). In the event that CB-839/placebo dosing is interrupted within 3 days before visits with PK sampling, PK samples should be collected during the next visit that the patient is in the clinic and has taken at least 3 consecutive days of CB-839/placebo. Please consult with the Medical Monitor to determine best options for making up missed PK samples.

Refer to the laboratory manual for details on collection kits and sample processing.

10.6.12 Pregnancy, Contraception and Nursing/Breast-feeding

Patients should be informed that taking the study drugs may involve unknown risks to a fetus (unborn baby) if pregnancy were to occur during study treatment exposure. In order to participate in the study, patients must adhere to pregnancy testing and contraception requirements described below ([Clinical Trial Facilitation Group 2014](#)).

10.6.12.1 Pregnancy Testing

All women who are being considered for participation in the study, and who are not surgically sterilized or postmenopausal (defined as without menses for >1 year without an alternative medical cause), will have a serum or urine pregnancy test during screening, on C1D1 predose (if screening test >3 days before receiving the first dose of study treatment), and at the End of Treatment Visit. If a urine test is positive or borderline (unable to confirm as negative), a serum β -hCG test will be required. Patients must be excluded in the event of a positive or borderline test result that is not confirmed as negative. Patients who become pregnant on study will be required to discontinue study treatment. Pregnancies occurring during and up to 6 months after completion of study treatment will be reported and followed for outcomes (see [Section 15.1](#)).

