- Is readily explained by and considered by the Principal Investigator to be an expected complication of the patient's primary malignancy, clinical state, concurrent medical conditions, or by other modes of therapy administered to the patient

A **protocol-related adverse event** is an AE occurring during a clinical study that is not related to the test article, but is considered by the Investigator or the Medical Monitor (or designee) to be related to the research conditions, i.e., related to the fact that a patient is participating in the study. For example, a protocol-related AE may be an untoward event occurring during a washout period or an event related to a medical procedure required by the protocol.

Other Reportable Information: certain events, although not considered an SAE, must be recorded, reported, and followed up within the same timelines as for an SAE. These events include:

- A case involving a pregnancy exposure to a test article, unless the product is indicated for use during pregnancy e.g., prenatal vitamins. Information about use in pregnancy encompasses the entire course of pregnancy and delivery and perinatal and neonatal outcomes, even if there were no abnormal findings. If a pregnancy is confirmed, test article must be discontinued immediately. All reports of pregnancy must be followed for information about the course of the pregnancy and delivery, as well as the condition of the newborn. When the newborn is healthy, additional follow-up is not needed. Pregnancies occurring up to 6 months after completion of the study treatment must also be reported to the Investigator.

- Overdose and abuse (e.g., a dose higher than that indicated in the protocol) with or without an AE. Overdose and/or abuse are not considered SAEs, but should be reported to the Sponsor expeditiously (within 24 hours of awareness). Overdose and/or abuse should be recorded as an AE in the eCRF and reported to Safety as a non-serious Grade 1 AE using the SAE Report form (by checking the “not applicable” box in the seriousness criterion). If the overdose and/or abuse is/are associated with the following:
 - An AE: both the term overdose or abuse and the associated AE should be recorded in the eCRF as AEs
 - SAE: the term overdose or abuse should continue to be recorded as a non-serious AE in both the eCRF and the SAE report form. In addition, an SAE associated with the overdose/abuse should be reported as an SAE in the SAE Report Form.

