ATTACHMENT 1: SCHEDULE OF STUDY ASSESSMENTS

(1 cycle = 28 days)	Pre-randomization	Post-randomization (Cycle dates are fixed relative to C1D1 and do NOT shift for dose interruptions)			
		Screening ¹	Cycle 1	Cycle 2+	Cycle 13+ (Every 3 cycles) ²
Assessments	≤ 28 days prior to randomization unless otherwise specified	Day 1 (≤ 3 days post randomization) ³	Day 1 (± 5 days)	Day 1 (± 7 days)	28 days (+7 days) after treatment discontinuation ⁴
Written Informed Consent	X ¹				
Inclusion/Exclusion Criteria	X				
Demographics and Medical History	X				
Physical Examination ⁵	X	X ³	X	X	X
Height	X				
Weight	X	X ³	X	X	X
Vital Signs ⁶	X	X ³	X	X	X
Karnofsky Performance Status	X	X ³	X	X	X
12-lead ECG ⁷	X		X ⁷	X ⁷	
Urinalysis ⁸	X	X ^{3,8}	X ⁸	X ⁸	X ⁸
Coagulation Tests ⁹	X				
Thyroid Function Tests ¹⁰	X		Every 2 cycles for Cycles 3-13, then as clinically indicated		X
Serum Chemistry	X	X ³	X	X	X
Hematology	X	X ³	X	X	X
Serum or Urine Pregnancy Test ¹¹	X	X ¹¹			X
PK Sample ¹²			X ¹²		
CB-839 or Placebo Dosing and Accountability/Compliance		CB-839 or Placebo will be administered twice daily (BID) with food and accountability taken through EOT Visit			
Cabozantinib Dosing and Accountability/Compliance		Cabozantinib will be administered once daily (QD) without food and accountability taken through EOT Visit			
Optional Tumor Biopsy ¹³		See Section 10.6.10.2 for details			
Archival Tumor Collection	X				

(1 cycle = 28 days)	Pre-randomization	Post-randomization (Cycle dates are fixed relative to C1D1 and do NOT shift for dose interruptions)			
		Visit	Screening ¹	Cycle 1	Cycle 2+
Assessments	≤ 28 days prior to randomization unless otherwise specified	Day 1 (≤3 days post randomization) ³	Day 1 (± 5 days)	Day 1 (± 7 days)	28 days (+7 days) after treatment discontinuation ⁴
Radiographic Evaluation of Tumor Burden	X ¹⁴		Every 8 weeks (± 5 days) ¹⁵	Every 12 weeks (± 7 days) ¹⁵	X ¹⁶
QoL Questionnaires		X	Every 4 weeks (± 5 days) ¹⁵	Every 12 weeks (± 7 days) ¹⁵	X ¹⁶
Adverse Events		Adverse event information will be collected at all study visits and may also be collected via any other forms of communication any time during the study. See Section 15.0 for additional details.			
Concomitant Medications	Concomitant medication information will be collected at all study visits and may also be collected via any other forms of communication any time during the study. See Section 10.1.1 for details				
Survival Follow-up					X ¹⁷

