- ¹¹ Pregnancy testing is required of all females of child-bearing potential. A negative pregnancy test during screening and within 3 days prior to the first dose of study treatment is required. Pregnancy testing on C1D1 is not required if the screening pregnancy test is ≤3 days before the first dose. If a urine test is positive or borderline (unable to confirm as negative), a serum β-hCG test will be required.

- ¹² PK samples are collected on C2D1: pre-dose and 2 hr post dose, and on C3D1: 4 hr and 6 hr post dose. Refer to the laboratory manual for detailed instructions on samples kits, collection, and shipment to a central laboratory. Contact Sponsor for guidance on options for collecting missed samples.
- ¹³ Optional tumor biopsies to be collected as clinically indicated from patients at North American sites only.
- ¹⁴ Screening tumor assessments within 28 days prior to randomization accepted. Radiographic assessments should include brain MRI for patients with history of brain metastases or suggestive symptoms and bone scan (bone scintigraphy) for patients with history of bone metastases or suggestive symptoms.
- ¹⁵ Radiographic tumor assessments and QoL questionnaires will be performed at the scheduled intervals *relative to the date of C1D1* regardless of study treatment holds or delays (note that treatment cycles are fixed and do not shift as a result of dose interruptions).
- ¹⁶ Unless performed within the previous 4 weeks (Note: patients who discontinue study treatment for reasons other than progressive disease [PD] or death will continue to be followed by radiographic tumor imaging until documentation of radiographic PD per RECIST v.1.1, death, initiation of a new anticancer therapy, or withdrawal of consent.)
- ¹⁷ Patients will be contacted every 3 mo for the first 12 mo after discontinuation of all study treatments (CB-839/placebo and cabozantinib) and every 6 mo thereafter for survival follow-up.

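### No pregnancy test is scheduled during dosing, so the mandatory stop-on-pregnancy rule has no routine trigger; a urine test at existing Day 1 visits would supply one.

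*Protocol*

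**What the plan says.** Section 10.6.12.1 of the protocol places pregnancy tests at screening, "on C1D1 predose (if screening test >3 days before receiving the first dose of study treatment), and at the End of Treatment Visit". A positive or borderline urine result goes to serum beta-hCG. Footnote 11 of Attachment 1 states the entry condition: "A negative pregnancy test during screening and within 3 days prior to the first dose of study treatment is required". The schedule row headed "Serum or Urine Pregnancy Test" is marked at Screening, Cycle 1 Day 1 and the End of Treatment Visit, and nowhere else. The End of Treatment column is timed at "28 days (+7 days) after treatment discontinuation".

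The consequence of a pregnancy is mandatory. Section 10.6.12.1 says "Patients who become pregnant on study will be required to discontinue study treatment". Section 15.1 says "If a pregnancy is confirmed, test article must be discontinued immediately". Section 11.3 lists pregnancy among the reasons for discontinuation.

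After treatment there is a reporting duty: "Pregnancies occurring during and up to 6 months after completion of study treatment will be reported and followed for outcomes", repeated in Section 15.1 as "Pregnancies occurring up to 6 months after completion of the study treatment must also be reported to the Investigator".

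**The concern.** The stop rule acts on a confirmed pregnancy, but nothing scheduled between first and last dose is designed to confirm one. The next scheduled test after Cycle 1 Day 1 nominally falls about a month after dosing has ended, when stopping is no longer a decision to be made.

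The hazard is acknowledged in the protocol. Section 11.1.2 names embryo-fetal toxicity for cabozantinib, and Section 10.6.12 speaks of unknown fetal risk from the study drugs. Section 10.6.12.2 also warns that hormonal contraception may work less well on study treatment.

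Clinical suspicion is a weak substitute for a test. Nausea, vomiting and fatigue, which can accompany early pregnancy, are also common drug effects: Table 9.5-2 gives 30.8%, 23.1% and 38.5% of 13 patients on the combination. The question that Section 15.2 requires at visits is a general one about how the patient has felt.

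What is at stake is the length of fetal exposure to study drug before anyone knows of the pregnancy.

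**Working it through.** The plan states no figure on this point, so there is none to reproduce. The check is a comparison of texts followed by date arithmetic.

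**Texts side by side**

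- Section 10.6.12.1: screening, predose on Cycle 1 Day 1 (waived if the screening test is recent enough), End of Treatment.
- Attachment 1 row: the same three columns; Cycle 2+ and Cycle 13+ are empty.
- Attachment 1 footnote 11: governs the test before first dose and adds no on-treatment test.
- Result: the three places agree. Scheduled tests between first and last dose: 0.

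**Inputs**

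- Design median PFS: 8 months (control) and 11.6 months (experimental), Sections 14.6.1 and 14.8. These stand in for dosing duration; that is an assumption.
- End of Treatment Visit: 28 to 35 days after discontinuation, Attachment 1.
- Visit windows: ±5 days for Cycle 2+ and ±7 days for Cycle 13+, with visits every 3 cycles (84 days) from Cycle 13, Attachment 1.
- Cycle length 28 days; 1 month = 30.4375 days, the SAP's conversion.

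**Gap now** = dosing duration + (28 to 35 days)

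- Control: 8 × 30.4375 = 243.5; 243.5 + 28 = 271.5 and 243.5 + 35 = 278.5, so about 272–279 days.
- Experimental: 11.6 × 30.4375 = 353.1; 353.1 + 28 = 381.1 and 353.1 + 35 = 388.1, so about 381–388 days.
- Add up to 3 days if the screening test stands in for Cycle 1 Day 1.

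**Day 1 visits passed without a pregnancy test** = whole 28-day cycles completed

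- 243.5 / 28 = 8.7, so 8 visits.
- 353.1 / 28 = 12.6, so 12 visits, the last being Cycle 13 Day 1 at day 336.

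Urinalysis is already marked for every one of these visits (Attachment 1, footnote 8).

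**Longest gap with a urine test at each Day 1 visit**

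- Within Cycles 2–12: 28 + 5 + 5 = 38 days.
- Cycle 12 Day 1 to Cycle 13 Day 1: 28 + 5 + 7 = 40 days.
- From Cycle 13: 84 + 7 + 7 = 98 days.
- Last on-treatment test to End of Treatment test, if dosing stops just before the next visit: 38 + 35 = 73 days; 40 + 35 = 75 days around Cycle 13; 98 + 35 = 133 days thereafter. Part of each of these intervals is off drug.

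**After treatment**

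- Six-month reporting window: 6 × 30.4375 = 182.6 days. After the End of Treatment test, 182.6 − 35 = 147.6 to 182.6 − 28 = 154.6 days remain.
- Four-month contraception period (Section 10.6.12.2): 4 × 30.4375 = 121.75 days. After the same test, 121.75 − 35 = 86.75 to 121.75 − 28 = 93.75 days remain.

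**The case against.** The strongest reply is that the schedule is a deliberate, internally consistent choice backed by other controls. Section 10.6.12.2 requires dual contraception with at least one highly effective method and bars entry where compliance is doubtful. Section 11.3 allows discontinuation for refusing contraception. Section 10.3 calls for a suitability review at each visit, and Section 10.6 permits extra assessments when clinically indicated. These controls stand: they lower the chance of a pregnancy or allow a suspected one to be tested. None of them schedules a test.

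A reader might infer that a pregnancy during dosing could surface only through self-report or a clinically indicated test. The documents do not support that. CT or MRI of the chest, abdomen and pelvis is scheduled every 8 weeks and then every 12 weeks (Sections 10.3 and 10.6.9), and a physical examination, symptom-directed on treatment, is scheduled at each visit (Section 10.6.2). Either could reveal a pregnancy. But neither is a pregnancy test, and detection that way would be incidental and probably late.

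A reader might also take the 28–35 days before the End of Treatment test as a firm minimum. It is nominal. Footnote 4 of Attachment 1 ends safety follow-up earlier if new anticancer therapy begins, and Section 11.3 records the decision date and the last-dose date separately.

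Section 11.1.3.2 tells sites to follow current cabozantinib prescribing information, and Section 10.6.12 cites a guidance on pregnancy testing. Neither source is available here, so neither can be credited with extra tests or used to show a departure.

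Finally, a reader might infer that the six months after treatment go unmonitored. They do not. The End of Treatment test falls inside that window, the reporting duty covers all of it, and contraception is required for four months. What is absent is an active prompt, since Section 10.4 names only survival status and subsequent therapy for the follow-up contacts. That is a smaller matter and not part of the main point.

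**Conclusion.** The point holds for the dosing period. No pregnancy test is scheduled between first and last dose, although the protocol names a fetal hazard for a drug taken in both arms and makes stopping mandatory. On the assumption that dosing lasts the design median PFS, scheduled tests are nominally about 9 to 13 months apart. Actual dosing may be shorter because of toxicity, or longer where treatment continues beyond progression (Section 11.3).

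These figures are calendar time between tests, not risk. The number of women of childbearing potential is not stated, so no number of pregnancies or avoided exposures is claimed. The testing provisions do not contradict each other; this is a design choice that can be improved. Sample size, power, type I error and the primary PFS analysis are unaffected. Consent pages were not available, and nothing is said about them.

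**What to change.** In Section 10.6.12.1 and Attachment 1, add a urine pregnancy test for women of childbearing potential at the Cycle 2+ and Cycle 13+ Day 1 visits, using the urine already scheduled for the proteinuria check. Keep the existing rule that a positive or borderline result goes to serum beta-hCG.

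The cost is one dip test per visit and slightly more site work, with no new visit or sample. It requires a protocol amendment under Section 18.0. The SAP describes randomization and enrolment in the past tense (SAP Sections 4 and 4.2); if enrolment is complete, only patients still on treatment would benefit. The interval would remain about 12 weeks from Cycle 13.

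Optionally, a pregnancy question could be added to the follow-up contacts at about 3 and 6 months after treatment. It should be put to the patient directly, because Section 10.4 allows contact through authorized third parties. It would be prompted self-report, supporting the existing six-month reporting duty, and would not be a test.

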10.6.12.2 Contraception

Sexually active patients with heterosexual partners must agree that they and their partners will use dual methods of contraception to prevent pregnancy during the course of study treatment and through 4 months after the last dose of all study treatment. Surgically sterilized or postmenopausal female patients (no menses for > 1 year without an alternative medical cause) or male patients with surgically sterilized or postmenopausal female partners are exempt from these requirements. Patients who choose abstinence are exempt from a second method of contraception. Male patients must include a barrier method of contraception (preferably male condom) if sexually active with a female partner of childbearing potential.

Contraception must include at least one highly effective method. Highly effective methods of contraception include:

- combined (estrogen and progestogen containing) hormonal oral, intravaginal or transdermal contraception associated with inhibition of ovulation
- progestogen-only hormonal oral, injectable, or implantable contraception associated with inhibition of ovulation
- intrauterine device
- intrauterine hormone-releasing system
- vasectomised partner
- sexual abstinence

Additional acceptable methods of contraception that are not considered highly effective include:

- progestogen-only oral hormonal contraception, where inhibition of ovulation is not the primary mode of action
- male or female condom with or without spermicide
- cap, diaphragm or sponge with spermicide

The following birth control methods are considered unacceptable:

- periodic abstinence (calendar, symptothermal, post-ovulation methods)
- withdrawal (coitus interruptus)
- spermicides only
- lactational amenorrhoea method

Because the absence of pharmacokinetic interactions between hormonal contraception and study treatment cannot be guaranteed, patients should also be counselled that there is potential for hormonal contraception to be less effective. Therefore, if a hormonal contraception is chosen as the highly effective hormonal method, the second method of contraception should be a barrier method (preferably male condom).

Male patients must also agree to refrain from donating sperm during the study and for a minimum of 4 mo following the last dose of all study treatment.

If there is any question that a patient will not reliably comply with the requirements for contraception, that patient should not be entered into the study.

